1. INTRODUCTION

This study is a Phase 2, open-label, multicenter study designed to assess the clinical activity and safety of INCMGA00012 in participants with advanced solid tumors where the efficacy of PD-1 inhibitors has previously been established.

The purpose of this SAP is to provide details of the statistical analyses that have been outlined in the Protocol. The scope of this plan includes the interim and final analyses that are planned and will be executed by the Department of Biostatistics or designee. The analyses of PK and pharmacodynamics that will be executed by the Department of Clinical Pharmacokinetics and respectively, are not described in detail in this SAP.

2. STUDY INFORMATION, OBJECTIVES, AND ENDPOINTS

2.1. Protocol and Case Report Form Version

This SAP is based on INCMGA 0012-203 Protocol Amendment 3 dated 10 DEC 2019 and CRFs approved 10 JAN 2019. Unless superseded by an amendment, this SAP will be effective for all subsequent Protocol amendments and CRF versions.

2.2. Study Objectives and Endpoints

The study objective and endpoints are presented in Table 1.

Table 1: Objectives and Endpoints

Objectives	Endpoints		
Primary			
To assess the efficacy of INCMGA00012 in terms of the ORR in tumor types of interest.	ORR, defined as the percentage of participants having a CR or PR, according to RECIST v1.1 as determined by the investigator.		
Secondary			
To determine the DOR to INCMGA00012.	DOR, defined as the time from an initial objective response (CR or PR) according to RECIST v1.1 until first observation of documented disease progression as determined by investigator or death due to any cause.		
To determine the DCR.	DCR, defined as the proportion of participants with either an objective response (CR and PR) or SD, according to RECIST v1.1.		
To determine the PFS of INCMGA00012.	PFS, defined as the time from the start of therapy until disease progression, as determined by investigator or death due to any cause.		
To determine the OS of INCMGA00012.	OS, defined as the time from the start of therapy until death due to any cause.		

To evaluate the safety of INCMGA00012.	Safety, determined by the number of participants, frequency, duration, and severity of AEs, laboratory tests, vital signs, and ECGs.
To determine the PK of INCMAG00012 when administered as a 30-minute infusion.	The PK of INCMAG00012, including C_{max} , T_{max} , C_{min} , and AUC_t , will be summarized.

3. STUDY DESIGN

3.1. Overall Study Design

This study is a Phase 2, open-label, multicenter study designed to assess the clinical activity and safety of INCMGA00012 in participants with advanced solid tumors where the efficacy of PD-1 inhibitors has previously been established. Participants with the following tumor types will be enrolled into disease-specific cohorts:

- Treatment-naïve metastatic NSCLC with high PD-L1 expression (TPS \geq 50%) and no EGFR, ALK, or ROS activating genomic tumor aberrations.
- Locally-advanced or metastatic urothelial cancer in cisplatin ineligible participants (determined by the investigator) whose tumors express PD-L1 (CPS ≥ 10 of PD-L1).
- Unresectable or metastatic melanoma.
- Locally advanced or metastatic clear-cell RCC without prior systemic treatment. The
 primary endpoint is ORR according to RECIST v1.1 as determined by the
 investigator. The study consists of 3 periods: screening, study drug treatment, and
 follow-up.

3.2. Overall Study Duration

The study begins when the first participant signs the ICF. The end of the study is defined as the date of the last visit of the last participant in the study. Participants completing treatment or prematurely discontinuing the study drug will be followed for survival until death, withdrawal of consent, or the end of the study, whichever occurs first.

3.3. Randomization

Not applicable.

3.4. Control of Type I Error

There is no formal hypothesis testing in this study and no control of Type I error rate. Response rate as well as the associated 95% CI will be provided. For analysis of efficacy endpoints such as ORR and DCR, 2-sided 95% confidence level will be reported.

3.5. Sample Size Considerations

This study is planned as a signal-finding study for efficacy in tumor types of interest for future development. Approximately 30 participants are planned to be enrolled in each disease-specific cohort to provide a preliminary assessment of efficacy, safety, and PK. The response rate and 95% CIs based on numbers of responses among 30 participants are provided in Table 2.

Table 2: Response Rate and 95% Confidence Interval

Sample Size	Number of Responses	Response Rate (%)	95% CI (%)
30	3	10.0	2.1, 26.5
30	5	16.7	5.6, 34.7
30	7	23.3	9.9, 42.3
30	9	30.0	14.7, 49.4
30	11	36.7	19.9, 56.1
30	12	40.0	22.7, 59.4

3.6. Schedule of Assessments

Refer to Protocol Amendment 3 dated 10 DEC 2019 for a full description of all study procedures and assessment schedules for this study.

4. DATA HANDLING DEFINITIONS AND CONVENTIONS

4.1. Scheduled Study Evaluations and Study Periods

4.1.1. Study Drug and Dose Level

INCMGA00012 is the only study drug in this study. The dose level of INCMGA00012 is 500 mg Q4W in this study, administered as a 30-minute infusion.

4.1.2. Day 1

Day 1 is the date when the first dose of INCMGA00012 is administered.

4.1.3. Study Day

If a visit/reporting date is on or after Day 1, then the study day at the visit/reporting date will be calculated as

Day # = (Visit/Reporting Date - Day 1 date + 1).

If the visit/reporting date is before Day 1, then the study day at the visit/reporting date will be calculated as

Day # = (Visit/Reporting Date - Day 1 date).

A study day of –1 indicates 1 day before Day 1.

4.1.4. Baseline Value

Baseline is the last nonmissing assessment obtained before the first administration of INCMGA00012.

When scheduled assessments and unscheduled assessments occur on the same day and time of the assessment or time of first dose is not available, use the following convention to determine baseline:

- If both a scheduled and an unscheduled visit are available on the day of the first dose and the time is missing, use the scheduled assessment as baseline.
- If all scheduled assessments are missing on the day of the first dose and an unscheduled assessment is available, use the unscheduled assessment as baseline.

4.1.5. Handling of Missing and Incomplete Data

In general, values for missing data will not be imputed unless methods for handling missing data are specified in this section or relevant sections.

Partial disease/cancer diagnosis date will be handled as follows:

- If only the day is missing, then the imputed day will be the first of the month.
- If both the month and day are missing, then the imputed day and month will be 01 JAN.

For relevant efficacy endpoints, partial death date will be imputed as follows:

- If mmyyyy for the last contact date = mmyyyy for the death date, then the death date will be set to the day after the last contact date.
- If mmyyyy for the last contact date < mmyyyy for the death date, then the death date will be set to the first day of the death month.
- Otherwise, the partial death date will not be imputed.
- No imputation will be done if the date is completely missing.

For prior and concomitant medications, the start/stop dates recorded in the eCRF by the investigator and his or her research staff will be used to identify when a concomitant medication was taken during the study. Any missing start date must be queried for resolution. Unresolved missing start dates will be handled as follows:

- If the date is completely missing, the medication will be considered both prior and concomitant.
- If only the day is missing, and the last day of the month is before the first dose date on Day 1, then the concomitant medication will be considered as starting before Day 1, and the incomplete date will be imputed as the last day of the month.

- If only the day is missing, and the first day of the month is on or after the first dose date on Day 1, then the concomitant medication will be considered as starting on or after Day 1, and the incomplete date will be imputed as the first day of the month.
- If only the day is missing, and the month is equal to the month of the first dose date on Day 1, then the incomplete date will be imputed as the first day of the month.
- If both the month and day are missing, and the last day of the year is before the first dose date on Day 1, then the concomitant medication will be considered as starting before Day 1, and the incomplete date will be imputed as if it is the last day of the year. Otherwise, if the last day of the year is on or after the first dose date Day 1, the incomplete date will be imputed as if it is the first day of the year.
- If the imputed start date through the above procedure is after stop date recorded in the eCRF, then the imputed start date will be set equal to stop date.

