4.2.3. Prior and Concomitant Medication

Prior medication is defined as any nonstudy medication started before the first dose of INCMGA00012.

Concomitant medication is defined as any nonstudy medication that is started accordingly:

- Before the date of first administration of INCMGA00012 and is ongoing throughout the study or ends on/after the date and time of first study drug administration.
- On/after the date of first administration of INCMGA00012 and is ongoing or ends during the course of study drug administration.

A medication could also be classified as "both prior and concomitant medication" if the end date is on or after the date of first administration of INCMGA00012. In the listing, it will be indicated whether a medication is prior-only, concomitant-only, or both prior and concomitant medication.

For the purposes of analysis, all medications will be considered concomitant medications unless the medications can unequivocally be defined as not concomitant (ie, if start date and end date are all missing, then the medication is considered as concomitant medication). See Section 4.1.5 for handling if missing/incomplete data.

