6.5. Prior and Concomitant Medication

Prior medications and concomitant medications will be coded using the WHO Drug Dictionary and summarized by WHO drug class and WHO drug term. Results will be summarized as number and percentage of participants with prior and concomitant medications by WHO drug class in the FAS. For the summary of concomitant medication, only medications starting on or after the first dose of study drug and no later than 90 days after the last dose of INCMGA00012 will be included. Medications with missing start/end date will be considered as concomitant medications in summary. Other medications will be provided in the listing. Medications intended to manage irAEs as well as prophylaxis/premedication used to prevent infusion reactions may be summarized separately. Post-therapy and nondrug therapy will also be listed per CRF.

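### Partial medication start dates in the first-dose month or year are imputed to before Day 1, giving on-study drugs a false prior flag and possibly dropping them from the concomitant summary

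*SAP*

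**What the plan says.** Four pieces of the SAP act together.

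- **Query step (4.1.5).** "Any missing start date must be queried for resolution". The imputation rules apply only to what remains, under the lead-in "Unresolved missing start dates will be handled as follows". That lead-in covers completely missing and partial dates alike.
- **Imputation (4.1.5).** A completely missing start makes the drug both prior and concomitant. If only the day is missing and the month is the "month of the first dose date on Day 1, then the incomplete date will be imputed as the first day of the month". If day and month are both missing and the year does not end before first dose, "the incomplete date will be imputed as if it is the first day of the year". An imputed start that falls after the recorded stop date is pulled back to the stop date.
- **Classification (4.2.3).** "Prior medication is defined as any nonstudy medication started before the first dose of INCMGA00012". A drug may carry both labels "if the end date is on or after the date of first administration of INCMGA00012". The default is that "all medications will be considered concomitant medications unless the medications can unequivocally be defined as not concomitant".
- **Summary filter (6.5).** The concomitant summary (Appendix A, Table 1.4.2) takes "only medications starting on or after the first dose of study drug and no later than 90 days after the last dose of INCMGA00012". The next sentence counts medications whose start/end date is missing as concomitant in the summary. Everything else goes to the listing.

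**The concern.** The other partial-date rules in 4.1.5 either place a start that can lie on only one side of Day 1, or leave a wholly unknown start with both labels. The two rules at issue take a start that could lie on either side and nearly always put it before Day 1. The error runs one way: prior use can only be overstated and on-study use can only be understated.

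The result is also out of order. A record with no start date at all is both prior and concomitant and stays in the concomitant summary. A record that carries more information, namely that the drug began in the month of first dose, can be dropped from that summary. This sits badly with the 4.2.3 default, since a start somewhere in the first-dose month is not unequivocally outside the treatment period.

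At stake is how accurately the medication tables describe use around the start of treatment, and whether two programmers working from this SAP would produce the same Table 1.4.2.

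**Working it through.** The plan states no figure on this point, so there is none to reproduce. The inputs are the rules above. Because the documents give no count of partial dates, I assume that first-dose dates and true start dates are spread uniformly over the calendar.

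**1. How often the imputed start precedes Day 1** (first doses over the 365 days of 2019)

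- Day missing, first-dose month: the imputed date is the 1st, which is before Day 1 unless Day 1 is the 1st. (365 − 12)/365 = 353/365 = 96.7%.
- Day and month missing, first-dose year: the imputed date is 1 January. (365 − 1)/365 = 364/365 = 99.7%.

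**2. What share of these records are on-study starts moved before Day 1**

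For Day 1 on day d of a 30-day month, the share of possible start days on or after Day 1 is (30 − d + 1)/30.

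| Day 1 on | Share truly on study |
|---|---|
| 2nd | 29/30 = 97% |
| 15th | 16/30 = 53% |
| 28th | 3/30 = 10% |

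Summing over d = 1 to 30 gives 465/900 = 52% truly on study. When d = 1 the imputed date equals Day 1, so nothing is moved and those 30 must come out: (465 − 30)/900 = 435/900 = 48%. Running the actual 2019 calendar also gives 48%.

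For year-only dates in a 365-day year, the same reasoning gives (365 × 366/2 − 365)/365² = 66,430/133,225, about 50%.

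**3. An example with first dose on 15 June 2019**

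| Recorded start | Imputed start | Side of Day 1 |
|---|---|---|
| June 2019 | 1 June 2019 | before |
| 2019 | 1 January 2019 | before |
| July 2019 | 1 July 2019 | after |
| 2020 | 1 January 2020 | after |

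**4. Following an on-study drug recorded as June 2019**

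- *Prior flag:* the imputed 1 June start meets the 4.2.3 definition of prior, so the drug is counted in Table 1.4.1.
- *Concomitant flag:* a drug truly begun on study ends on or after Day 1 or is ongoing. Under 4.2.3 it is therefore both prior and concomitant in the listing.
- *Table 1.4.2:* the imputed start fails the 6.5 filter. Whether the record is restored depends on whether a partial date is a missing date in the next sentence of 6.5. The lead-in in 4.1.5 suggests yes. Two things suggest no. The parenthesis in 4.2.3 illustrates doubt with start and end dates both missing. And if every partial date counted as missing, a start imputed to a month wholly before Day 1 would be swept in too, leaving imputed starts no role in that filter.

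**The case against.** The strongest reply has four parts.

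- **The drugs are not lost as concomitant.** A reader might infer that they become prior-only. That is wrong: 4.2.3 gives them both labels, the same result that 4.1.5 gives a completely missing date. This part stands in full for the listing.
- **Exclusion from Table 1.4.2 is not certain.** A reader might take it as a direct result of 4.1.5. It comes from the 6.5 filter, and only if the missing-date sentence is read narrowly. This stands as a limit on the claim. It does not remove the problem, because the SAP leaves the reading open.
- **Imputing to Day 1 would be no better.** Under the same uniform assumption, (d − 1)/30 of day-missing records truly began earlier: 4/30 = 13%, 14/30 = 47% and 24/30 = 80% for Day 1 on the 5th, 15th and 25th. Unless their stop date preceded Day 1, these would wrongly lose prior status. This stands, and it shapes the remedy below.
- **The practical effect may be small.** Medications are reviewed at every cycle visit (Protocol Table 3), missing starts are queried, and 6.5 allows separate summaries of drugs for immune-related events and of infusion premedication. Nothing in the documents shows that drugs for early toxicity are especially likely to lack a day. This also stands.

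**Conclusion.** The point holds in a limited form. The two rules in 4.1.5 put a start that could lie on either side of Day 1 before it, except when Day 1 is the 1st of the month or 1 January. For a drug truly begun on study, the false prior flag follows with no disputed reading. Loss from Table 1.4.2 follows on the more natural reading of 6.5, but the SAP does not settle it.

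Under uniform dates, about 48% of day-missing records in the first-dose month, and about 50% of year-only records in the first-dose year, are on-study starts moved before Day 1. In a 30-day month the share runs from 97% to 10% for Day 1 from the 2nd to the 28th. These are shares of affected records, not of all medications, and the number of affected records is unknown.

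A reader might go further and suspect an effect on response rate or other efficacy results. The documents do not support that: no efficacy endpoint is defined through this rule. The issue is minor and confined to descriptive medication tables and to dates unresolved after query.

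**What to change.** Make two small changes to the SAP.

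1. **In 4.1.5:** treat a partial start date that could fall on either side of Day 1 in the same way as a completely missing one. The drug is both prior and concomitant, unless its recorded stop date is before Day 1, in which case it is prior-only. The other rules stay as they are.
2. **In 6.5:** state that such records, when not prior-only, are included in the concomitant summary regardless of the imputed date.

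The records remain in Table 1.4.1, but under a dual label that openly reflects an unknown start. Their place in Table 1.4.2 no longer depends on how a programmer reads the word missing.

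The cost is a clause in each section and a small change to the derivation code. The small downside is that some drugs begun before Day 1 and continued on study will appear in the concomitant summary, which is the direction that 4.2.3 already prefers.

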4.1.6. Cycle Length and Duration

One cycle is 28 days (4 weeks) for all participants in this study. Cycle 1 Day 1 is the day the first infusion of INCMGA00012, with the exception for records of clinical laboratory tests, vital signs, and ECGs, where visit Cycle 1 Day 1 could be within 7 days before the day of first infusion of INCMGA00012. Day 1 of subsequent cycles will correspond to the infusion date of INCMGA00012 within the cycle. Tumor assessments follow Protocol-defined schedule, that is, Q8W with \pm 7-day window within 1 year and Q12W with \pm 14-day window after 1 year. Analysis of tumor response assessments follow the same time window.

4.1.7. On-Treatment Assessment/Event

Safety summaries and selected summaries of deaths will summarize only on-treatment assessments/events. On-treatment assessment/event is defined as any assessment/event obtained in the time interval:

 Date of first infusion of INCMGA00012 through date of last infusion of INCMGA00012 + 90 days;

Adverse events that begin or worsen after informed consent obtained should be recorded in the Adverse Events CRF.

If the last date of study drug administration is missing, on-treatment assessments/events include any assessment/event recorded in the database and those that occur after the start date of study drug unless there are other datasets indicating treatment is ended.

Data listings will include all assessments/events, flagging those that are not on-treatment assessments/events.

